1.0 Objectives

1.1 Describe the purpose, specific aims, or objectives of this research.

Response: To study the effects of transcranial direct current stimulation (tDCS) on weight and appetite.

Aim:

- 1. To compare weight loss over one month in active tDCS group with sham tDCS group. We will measure weight of every participants at the beginning of the study and one month after the last session of tDCS*
- 2. To compare change in insulin sensitivity over one month in active tDCS group with sham tDCS group. We will measure fasting insulin and glucose level, and calculate homeostatic model assessment-insulin resistance (HOMA-IR)*
- 3. To compare change in cognitive performance as a response to food over one month in active tDCS group with sham tDCS group. We will evaluate performance in a computerized task that measures executive functions under the presence of food (working memory, inhibitory control and a combination of both). We will assess changes in accuracy and speed in the task under active tDCS versus sham tDCS.*
- 4. To compare change in post-prandial glucose excursion and average meal counts per day. We will use continuous glucose monitor to record the frequency and amplitude of glucose excursion.*

1.2 State the hypotheses to be tested, if applicable.

NOTE: A hypothesis is a specific, testable prediction about what you expect to happen in your study that corresponds with your above listed objectives.

Response:

Hypothesis:

- 1. Active tDCS will result in more weight loss, appetite reduction and improved insulin sensitivity compared with sham tDCS over one month period.*
- 2. The effect of tDCS on weight, appetite, glucose tolerance and cognitive response to food varies according to the underlying allele status of BDNF and COMT gene*

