2.0 Scientific Endpoints

2.1 Describe the scientific endpoint(s), the main result or occurrence under study.

*NOTE: Scientific endpoints are outcomes defined before the study begins to determine whether the objectives of the study have been met and to draw conclusions from the data. Include primary and secondary endpoints. Some example endpoints are: reduction of symptoms, improvement in quality of life, or survival. Your response should **not** be a date.*

Response:

Primary endpoints: change in weight, measured as a percentage of baseline body weight.

Secondary endpoints: change in HOMA-IR, change in average daily meal counts based on frequency of glucose excursion on continuous glucose monitor, change in average amplitude of glucose excursion curve after meals, change in cognitive performance in response to food

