10.0 Procedures Involved

10.1 *Provide a description of all research procedures or activities being performed and when they are performed once a subject is screened and determined to be eligible. Provide as much detail as possible.*

NOTE: This should serve as a blueprint for your study and include enough detail so that another investigator could pick up your protocol and replicate the research. For studies that have multiple or complex visits or procedures, consider the addition of a schedule of events table in in your response.

Screening Day

All subjects will have completed the following procedures prior to participating in the study:

- 1) Informed consent
- 2) Medical history
- 3) Physical exam (including body mass index measurement)

We will collect general demographic data regarding years of education, race/ethnicity.

A continuous glucose monitor will be calibrated with finger blood glucose result and the probe of the monitor will be inserted into the abdominal subcutaneous tissue. Patient will be instructed on how to use continuous glucose monitor, they will be instructed to wear it and document the time and the types of food of every meal for at least 72 hours after the screening visit.

Subjects will be instructed not to change their medications during the whole study period and not to take insulin for at least 4 hours before visit 1, visit 5 and visit 6.

Visit 1:

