Subjects assigned to sham tDCS group will receive 15 seconds of anodal tDCS delivered with a neuroConnVR DCSTIMULATOR device (neuroConn GmbH, Ilmenau, Germany), at a constant current of 2 mA (with a 30-second ramp at on- and offset) using two sponge electrodes soaked in a sterile 0.9% sodium chloride solution. However, they will stay at the research center for 30 minutes with electrodes on their scalp. Before starting the stimulation, a code will need to be entered into the tDCS machine which will decide whether a sham or active stimulation will be performed by the machine automatically in the next 30 minutes. At the beginning of the study, a code that is associated with either active stimulation or sham stimulation will be assigned to the subject based on the randomization. However, neither the subject or the operator of tDCS machine will know what does the code represent.

Visit 2: Subjects will come back next day to receive the second session of the same intervention.

Visit 3: Subjects will come back next day to receive the third session of the same intervention.

Visit 4: Subjects will come back next day to receive the fourth session of the same intervention.

Visit 5: Subjects will fast overnight (10 hours) and come back next morning at 7 to 7:30 AM to receive the fifth session of the same intervention. We will then measure body mass index, plasma insulin and glucose, appetite and cognitive function in response to food. Continuous glucose monitor will be reinstalled, and subjects will be instructed to wear it and document the time and types of food of every meal for at least 72 hours after this visit and 72 hours before the next visit. Subject will be instructed on how to insert and remove continuous glucose monitor again.

Visit 6: Subjects will fast overnight (10 hours) and come back next morning at 7 to 7:30 AM in 4 weeks after visit 5. We will measure body mass index, plasma insulin and glucose, appetite and cognitive function in response to food again. We will download data from the continuous glucose monitor. We will also ask if the subject believed that he/she received active or sham tDCS.

10.2 Describe what data will be collected.

NOTE: For studies with multiple data collection points or long-term follow up, consider the addition of a schedule or table in your response.

Response:

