We will collect general demographic data regarding years of education, race/ethnicity. We will also administer the three-factor eating questionnaire (Stunkard and Messick, 1985), which measures eating habits and attitudes toward food, weight and dieting, and a personality questionnaire, the Big Five (Costa and McCrae, 1989).

Plasma glucose and insulin level during screening visit, visit 5 and visit 6

COMT and BDNF gene during screening visit

Weight, height and body mass index (BMI) during screening visit, visit 5 and visit 6
Cognitive response to food during screening visit, visit 5 and visit 6.
Average daily meal counts and type of food based on patient report and continuous glucose meter on visit 1 and visit 6

10.3 *List any instruments or measurement tools used to collect data (e.g. questionnaire, interview guide, validated instrument, data collection form).*

Include copies of these documents with your submission.

Response: Please see form for screening visit, form for follow up visit 1, 2, 5 and 6, eating habit questionnaire, personality questionnaire.

Describe any source records that will be used to collect data about subjects (e.g. school records, electronic medical records).

Response: electronic medical records, clinical charts and research files

10.4 *Indicate whether or not **individual** subject results, such as results of investigational diagnostic tests, genetic tests, or incidental findings will be shared with subjects or others (e.g., the subject's primary care physician) and if so, describe how these will be shared.*

Response: Individual participant lab results will be disclosed to the participant upon their request. If the participant requests documentation be shared with another physician, physician office or hospital, the participant must come to the research center to collect said documentation and/or the documentation can be mailed to their given home address.

10.5 *Indicate whether or not **study** results will be shared with subjects or others, and if so, describe how these will be shared.*

Response: Study results will not be shared directly with subjects. However, study results could be published in the form of a manuscript, to an academic journal.

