11.0 Study Timelines

11.1 *Describe the anticipated duration needed to enroll all study subjects.*

Response: 10 weeks

11.2 *Describe the duration of an individual subject's participation in the study. Include length of study visits, and overall study follow-up time.*

Response: If the subject was found to meet the eligibility criteria, he/she will come to our research center for 6 appointments. Each appointment lasts for 1 hour and the total length of the study is about 2 months

11.3 *Describe the estimated duration for the investigators to complete this study (i.e. all data is collected and all analyses have been completed).*

Response: 18 months

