17.0 Data Management and Analysis

17.1 Describe the data analysis plan, including any statistical procedures. This section applies to both quantitative and qualitative analysis.

Response:

The demographic features of the population and screening lab results will be displayed in tables. Statistical analysis will be conducted using SigmaStat software version 3.1 (SPSS Inc., Chicago, IL). Data will be represented as mean \pm S.E. Sample size cannot be estimated as this is a pilot study. Generalized linear mixed model will be applied to compare the difference in weight, average amplitude of glucose excursion curve, average daily meal count, HOMA-IR, reaction time and percentage correct response in computerized cognitive tests. Predicting variables include time in the study (baseline, visit 5 and visit 6) and type of intervention (active tDCS vs sham). Sensitivity analysis will be performed to evaluate baseline imbalance, outliers, protocol violation, and missing data. The proposed covariants to be evaluated for baseline imbalance includes age, gender, COMT and BDNF gene status, baseline weight, baseline HOMA-IR, baseline average amplitude of glucose excursion curve, baseline average daily meal count, baseline reaction time and percentage correct response.

17.2 If applicable, provide a power analysis.

NOTE: This may not apply to certain types of studies, including chart/records reviews, survey studies, or observational studies. This question is asked to elicit whether the investigator has an adequate sample size to achieve the study objectives and justify a conclusion.

Response: This is a pilot study, so we are not able to estimate sample size. However, previous shorter term study showed a small effect of tDCS on appetite and weight (see reference 9) in nine patients. We consider that by recruiting 20 participants, it will be more likely to detect a significant change, while the total expense will still be within the limit of our fund.

17.3 Describe any procedures that will be used for quality control of collected data.

Response:

Date entered by research staff will be verified by another person independently.

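### No visit is named as baseline for the primary weight endpoint: 10.2 lists pre-treatment weight at a screening visit with no stated fast or clock time, and contradicts 10.1 on when labs, genes and cognition are first taken

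*Combined protocol and SAP*

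**What the plan says.** Section 2.1 defines the primary endpoint as "change in weight, measured as a percentage of baseline body weight" and names no visit for the denominator. The model in 17.1 is described as "Predicting variables include time in the study (baseline, visit 5 and visit 6"), with treatment arm as the other predictor. Baseline is again not tied to a visit.

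On weight, the protocol says the following:

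- 1.1, Aim 1: "We will measure weight of every participants at the beginning of the study and one month after the last session of tDCS".
- 10.1: BMI is part of the Screening Day physical examination and is measured again at Visits 5 and 6. The Visit 1 procedures mention neither weight nor BMI.
- 10.2: "Weight, height and body mass index (BMI) during screening visit, visit 5 and visit 6".
- 19.2: height and weight are monitored at every visit, as part of safety review.

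On conditions, 10.1 asks for a 10-hour overnight fast and arrival between 7 and 7:30 am at Visits 1, 5 and 6. It states neither for Screening Day. The instruction about insulin before a visit names Visits 1, 5 and 6 only. Visit 1 takes place within two weeks of screening.

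**The concern.** A percentage change depends on its reference value, and here that value can be read in two ways. If 10.2 is followed, a weight taken with no stated fast or time of day, up to two weeks before treatment, is compared with fasted early-morning weights at Visits 5 and 6. This adds weighing-condition noise to the primary endpoint. It also gives participants untreated lead-in periods of different lengths, and makes any within-arm change include untreated days and any difference in weighing conditions.

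For HOMA-IR the issue is sharper. Aim 2 calls for fasting insulin and glucose, but a screening sample would have no stated fast and no insulin instruction.

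If weight is in fact taken at every visit, as 19.2 indicates, two candidate baseline weights will exist and nothing in the plan says which one enters the analysis. With 20 participants and no power calculation, neither the noise nor the discretion is welcome.

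**Working it through.** **1. The sections side by side (pre-treatment assessment only)**

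| Measure | 10.1 | 10.2 |
|---|---|---|
| Weight/BMI | Screening Day (BMI); not listed at Visit 1 | Screening |
| Glucose and insulin | Visit 1, fasted | Screening |
| COMT and BDNF | Visit 1 | Screening |
| Cognitive task | Visit 1 | Screening |
| Meal counts | Monitor data downloaded at Visit 1 | Visit 1 |

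The two sections agree on weight and disagree on the next three rows.

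**2. Does Aim 1 settle the weight baseline?** Its wording could well mean Visit 1. Section 10.1 uses the same phrase for assigning the stimulation code, which follows randomisation at Visit 1: "At the beginning of the study, a code that is associated with either active stimulation or sham stimulation will be assigned to the subject". It introduces the screening procedures with "All subjects will have completed the following procedures prior to participating in the study", which places screening before the study. Section 11.2 says that, once eligible, "he/she will come to our research center for 6 appointments", which matches Visits 1 to 6. But the 10.2 list gives screening, not Visit 1, as the pre-treatment weighing, so the text is not settled.

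**3. Is the screening label in 10.2 just a loose name for Visit 1?** Not clearly. The same list dates meal counts at Visit 1, and 10.3 cites separate forms for the screening visit and for Visit 1.

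**4. Which visit do the laboratory samples belong to?** Three things favour Visit 1: Aim 2 asks for fasting values, the insulin instruction names Visits 1, 5 and 6, and Screening Day in 10.1 has no blood sample beyond a finger glucose to calibrate the monitor. One thing points the other way, in 17.1: "The demographic features of the population and screening lab results will be displayed in tables".

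**5. Days, from the nominal schedule with Visit 1 as day 0**

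- Visits 2 to 5 are on successive days, so Visit 5 is day 4. Visit 6 is four weeks later: 4 + 28 = day 32.
- The earliest screening is day −14. Screening to Visit 6 is then 14 + 32 = 46 days, of which 14/46 = 30% is untreated. The interval is 14/32 = 44% longer than from Visit 1.
- The latest screening is about day −3. This is inferred from at least 72 hours of monitor wear before the Visit 1 download. Screening to Visit 6 is then 3 + 32 = 35 days, 3/35 = 9% untreated and 3/32 = 9% longer.
- The spread between participants is up to 14 − 3 = 11 days.

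These are shares of calendar time, not of weight change.

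**6. Precision.** The documents give no standard deviation, effect size or power figure, so there is no stated figure to reproduce and the loss cannot be derived. For scale only, suppose percentage change from a standardised baseline has SD *s*, and an unstandardised baseline adds independent noise *e*. The SD becomes √(s² + e²). Assume 10 per arm, two-sided 5%, 80% power and a simple two-group comparison, so that the detectable difference is (1.96 + 0.84) × SD × √(2/10). With assumed s = 2.0 and e = 1.0 points, the SD rises to 2.24 and the detectable difference from 2.5 to 2.8 points. Over assumed ranges of s from 1.5 to 3.0 and e from 0.5 to 1.5, the 80% power falls to between 79% and 51%. The lowest figure needs noise as large as the SD itself. The conclusion does not rest on these assumed values.

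**The case against.** The strongest reply has five parts.

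- **Weight is not contradictory.** 10.1 and 10.2 both place it at screening, and a pre-randomisation screening weight can be a legitimate baseline. That is true, and no contradiction on weight is claimed. What remains is that no section calls that weight the baseline, no weighing conditions are stated for it, and 19.2 implies a second candidate.
- **The 10.2 list is incomplete.** It omits the treatment-guess question and the pregnancy test, for example, so its silence on a Visit 1 weight proves little. This weakens any inference from omission. It does not explain why the list positively assigns four measures to screening.
- **10.1 is the operational text and largely settles the laboratory and cognitive measures.** Staff following it would draw fasted samples at Visit 1. This is the likelier reading, but 10.2 and 17.1 both say screening, and a protocol should not leave staff to decide which section prevails.
- **The harm is limited.** The comparison is active against sham, so common untreated days do not bias it, and gene status does not change between visits. Both points stand.
- **The screening documents and visit forms cited in 8.1 and 10.3 might state the conditions.** They are not among the documents reviewed, so this cannot be excluded. Even so, 2.1 and 17.1 would still lack a named baseline, and 10.1 and 10.2 would still disagree.

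A further point is that 10.1 mentions randomisation ahead of the Visit 1 measurements, so a Visit 1 baseline may fall after allocation. With participant and operator blinded and the value taken before any stimulation, the effect should be negligible.

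**Conclusion.** The concern holds and should be fixed. The baseline for the primary endpoint is not tied to a visit. The only pre-treatment weight in the data list is at a visit with no stated fast or clock time. Sections 10.1 and 10.2 contradict each other on the first visit for glucose and insulin, genes and cognition.

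A screening baseline would stretch the 32-day interval to somewhere between 35 and 46 days, with 9% to 30% of it untreated. The upper end rests on the two-week limit in 10.1 and the lower end on the inferred three-day minimum. No between-arm bias is expected. The consequences are avoidable noise of unknown size, an untreated lead-in that differs between participants, and discretion over which baseline is analysed. For HOMA-IR there is also the possibility of a baseline sample without a stated fast. The gene mismatch is a consistency error without analytic effect. Confidence is high on the missing definition and the contradiction. How weight is actually taken at screening cannot be known without the visit forms.

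**What to change.** - In 2.1 and 17.1, define baseline for weight, HOMA-IR and cognition as the fasted Visit 1 value taken before the first stimulation.
- In 10.1, name weight among the Visit 1 procedures. Weighing on arrival, before randomisation, would also remove the question of order.
- In 10.2, change the screening label to Visit 1 for weight, glucose and insulin, genes and cognition.
- In 17.1, reword the reference to screening laboratory results to match.
- Use screening weight and BMI for eligibility only.

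The cost is protocol wording. The fasted Visit 1 blood draw and cognitive task are already scheduled in 10.1, and 19.2 already has weight monitored at every visit. If a Visit 1 weight is not in fact being taken, the fix adds one weighing at an existing visit. No visit or sample is added.

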11.0 Study Timelines

11.1 *Describe the anticipated duration needed to enroll all study subjects.*

Response: 10 weeks

11.2 *Describe the duration of an individual subject's participation in the study. Include length of study visits, and overall study follow-up time.*

Response: If the subject was found to meet the eligibility criteria, he/she will come to our research center for 6 appointments. Each appointment lasts for 1 hour and the total length of the study is about 2 months

11.3 *Describe the estimated duration for the investigators to complete this study (i.e. all data is collected and all analyses have been completed).*

Response: 18 months

12.0 Setting

12.1 Describe all facilities/sites where you will be conducting research procedures.

Include a description of the security and privacy of the facilities (e.g. locked facility, limited access, privacy barriers). Facility, department, and type of room are relevant. Do not abbreviate facility names.

NOTE: Examples of acceptable response may be: "A classroom setting in the Department of Psychology equipped with a computer with relevant survey administration software," "The angiogram suite at Buffalo General Medical Center, a fully accredited tertiary care institution within New York State with badge access," or, "Community Center meeting hall."

Response:

Research will be conducted at the Diabetes Endocrinology Research Center of WNY, located at [name]. The Diabetes Research Center has facilities and exam rooms available for insulin pump download, continuous glucose monitor device download, meal and infusion studies and presence of study coordinator and registered nurse for data collection and blood work at all times. One of the investigators will be available at all times to address patients' related issues. Equipment include ultra-low freezers for sample storage, centrifuges, microscopes for sample preparation, infusion pumps, ELISA, PCR and immunoblotting instrumentation. CTRC location is a fully equipped laboratory

12.2 For research conducted outside of UB and its affiliates, describe:

- *Site-specific regulations or customs affecting the research*
- *Local scientific and ethical review structure*

NOTE: This question is referring to UB affiliated research taking place outside UB, i.e. research conducted in the community, school-based research, international research, etc. It is not referring to multi-site research. UB affiliated institutions include Kaleida Health, ECMC, and Roswell Park Cancer Institute.

Response:

N/A: This study is not conducted outside of UB or its affiliates.

13.0 Community-Based Participatory Research

13.1 Describe involvement of the community in the design and conduct of the research.

NOTE: Community-Based Participatory Research (CBPR) is a collaborative approach to research that equitably involves all partners in the research process and recognizes the unique strengths that each brings. CBPR begins with a research topic of importance to the community, has the aim of combining knowledge with action and achieving social change to improve health outcomes and eliminate health disparities.

Response:

N/A: This study does not utilize CBPR.

13.2 Describe the composition and involvement of a community advisory board.

Response:

N/A: This study does not have a community advisory board.

